7.2 Measures to Adjust for Multiplicity, Confounders, Heterogeneity

We have two primary outcomes and so have adjusted the alpha for each primary outcome to 0.025 to give an overall alpha of 0.05 across both outcomes. We have several secondary outcomes. All secondary outcomes are exploratory and not powered for. We will therefore not adjust for multiple secondary outcomes but instead report all effect sizes, confidence intervals, and p values in order to let readers use their own judgment about the relative weight of the conclusions. This approach aligns with the usage of p-values favoured by the American Statistical Association. [Wasserstein RL, Schirm AL, Lazar NA. Moving to a world beyond “ $p < 0.05$ ”. *The American Statistician*. 2019; 73:1-19.]

8 Sensitivity Analyses

If multiple imputation is used for the primary outcomes, sensitivity analyses will be conducted on complete case analysis.

9 QC Plans

Data quality will be checked/promoted through a process of identifying extreme values and checking the source of these values in case of a data entry error. A record of any/all manual corrections to data will be maintained. Calculations of scores from multi-item scales will be carried out using Microsoft Excel functions and cross-checked using other statistical packages to reduce errors.

10 Programming Plans

A list of all tables, figures, listings and their templates can be found in Appendix 3.

11 References

vidEO study project proposal - V3

References as detailed or as per vidEO study project proposal - V3.

Appendix 1

VARIABLES IN THE DATA SET

Domain	Label	Measurement method	Details
Age	AGE	Calculated from date of birth	Reported in years
Gender	GENDER	Self-reported using the following categories: 
 – Male = 1 – Female = 2 – Other (please specify) / Prefer not to say = 3 – Non-binary = 4 	Number and proportion of participants responding to each category will be reported.
State/territory	STATE	Self-reported using the following categories: ACT, NSW, NT, QLD, SA, TAS, VIC, WA	N (%) in each category
Geographical location	LOCATION	Determined from self-reported residential postcode and classified according to the Australian Standard Geographical Classification (ASGC Remoteness Structure)	N (%) in each category of: major city, inner regional, outer regional, remote and very remote locations
Height	HEIGHT	Self-reported	Reported in metres
Weight	WEIGHT	Self-reported	Reported in kilograms
Body mass index	BMI	Calculated from height and weight.	Reported in kg/m ²
Level of education	EDUCATION	Self-reported using the following categories: 
 – Less than 3 years of secondary education (high school) – 3 or more years of secondary education (high school) – Some education beyond high school e.g., trade/technical/vocational training – Completed tertiary education (college or university) 	N (%) in each category
Current employment situation	EMPLOYMENT	Self-reported using the following categories: 
 – Unemployed/not employed/ e.g., full-time carer, full-time student 	N (%) in each category

		
 – Retired (not due to health reasons) – Unable to work due to health reasons – Paid work part time – Paid work full time 	
Ethnicity	ETHNICITY	
Self-reported using the following categories (choose only one representing the ethnicity you mostly identify with):
 
 – Australian/New Zealand – Aboriginal and Torres Strait Islander – European – Asian – Other Oceania – North African & Middle Eastern – Sub-Saharan Africa – North American – South American – Other (please list) 	N (%) in each category
Pain severity during walking (Bellamy, 1997)	SEVERITY	
Select the number on the following scale to show the average amount of pain felt during walking over the PAST WEEK in your most painful knee (0-10, where 0=no pain and 10=worst pain possible)
	Scored on an 11-point NRS for average pain on walking in the last week. Ranges from 0 to 10
Pain duration	DURATION	
Self-reported using the following categories:
 
 – Less than one year – One to two years – Two to five years – Five to ten years – Ten to fifteen years – Fifteen to twenty years – More than twenty years 	N (%) in each category
Where have you previously learned about osteoarthritis? (select all that apply)	INFORECEIVED	
 – No information received – GP or family doctor – Orthopaedic surgeon – Another doctor (such as sports doctor or rheumatologist) – Nurse – Physiotherapist – Osteopath – Chiropractor – OA rehabilitation programme – Arthritis educator – Arthritis support group – Other people with OA – Family or friends – Internet/website 	N (%) in each category

		
 – Television – Information booklets – Training as a health professional – Other media – Other health professional 	
Personal relevance	RELEVANCE	
Rated using a 5-point Likert scale: How relevant do you think education about knee osteoarthritis is to you at this time?
 
0=Not at all relevant 1=A little bit relevant 2=Quite relevant 3=Very relevant 4=Extremely relevant
	N (%) in each category

Continuous outcomes will be defined as change scores (subtraction arranged so that positive values indicate improvement, e.g., change in ASES-Pain and all secondary continuous outcomes with baseline measures (post-intervention minus baseline), change in BFMS (baseline minus post-intervention)).

Domain	Tool	Details
Primary outcome measures		
Arthritis Self-Efficacy Scale (Pain subscale) (Lorig et al., 1989)	
For each of the following questions, please circle the number that corresponds to how certain you are that you can do the following tasks regularly at the present time.
 
 1. How certain are you that you can decrease your pain quite a bit? 2. How certain are you that you can continue most of your daily activities? 3. How certain are you that you can keep arthritis pain from interfering with your sleep? 4. How certain are you that you can make a small-to-moderate reduction in your arthritis pain by using methods other than taking extra medication? 5. How certain are you that you can make a large 	
Scored with 5 questions, each via a 11-point NRS where 0=Very uncertain and 10=Very certain.
 
Scores are the mean of all the items in the subscale (range 0-10).
 
Higher scores indicate greater self-efficacy.

reduction in your arthritis pain by using methods other than taking extra medication?

Brief Fear of Movement Scale for Osteoarthritis

1. *I am afraid that I may injure myself if I exercise*
2. *If I were to try to overcome it, my pain would increase*
3. *I am afraid that I might injure myself accidentally*
4. *Simply being careful that I do not make unnecessary movements is the safest thing I can do to prevent pain from worsening*
5. *It's really not safe for a person with a condition like mine to be physically active*
6. *I can't do all the things normal people do because it's too easy to get injured*

Scored with 6 statements regarding fear of injury/re-injury due to movement, each via a 4-point Likert scale from 1=Strongly disagree to 4=Strongly agree. Scores range from 6 (minimal fear) to 24 (maximal fear).

Secondary outcome measures

Level of concern

Rated using a 5-point Likert scale:
How concerned are you about your knee problem?
 0=Not at all concerned
 1=A little concerned
 2=Quite concerned
 3=Very concerned
 4=Extremely concerned

N (%) in each category

Credibility/expectancy questionnaire
 (**bold** text are changes from original wording)

*We would like you to indicate below what you believe, right now, about **your knee problem**. The questionnaire consists of two parts. In the first part, you tell us what you think about managing your knee **problem**. In the second part, you tell us about your expectations and how you feel you will be in the future.*

Scores on item 5 transformed with a minimum of 1 and a maximum of 9, and a sum score formed for each factor ranging from 3 to 27 for Part 1 and 2 to 18 for Part 2.

Part I

1. *At this point, how logical does doing a lot of physical*

activity or exercise seem to you?

1=not at all logical,
5=somewhat logical,
9=very logical

2. At this point, how successful do you think **you can be** in reducing your **knee pain**?

1=not at all **successful**,
5=somewhat **successful**, 9=very **successful**

3. How confident would you be in recommending **physical activity** to a friend who experiences similar problems?

1=not at all confident,
5=somewhat confident, 9=very confident

Part II

For this part, close your eyes for a few moments, and try to identify what you really feel about your **knee problem**.

Then answer the following questions.

4. At this point, how much do you really feel that **doing as much physical activity as you can**, will help you to reduce your knee pain?

1=not at all,

5=somewhat, 9=very much

5. **In one year's time**, how much improvement in your **knee pain** do you really feel will occur?

-4 = a great deal

worse

-3 = quite a lot worse

-2 = moderately worse

-1 = a little worse

0 = about the same

1 = a little better

2 = moderately better

3 = quite a lot better

4 = a great deal better

Importance of physical activity

Role of physical activity. Please read each statement and select the option that indicates how much you agree or disagree with each statement.

- 1. Physical activity should be avoided because of my knee*
- 2. Being physically active won't change things for my knee*
- 3. Physical activity will help my knee quite a bit*
- 4. It is important for my knee to do as much physical activity as I can*

Four item Likert scale with 5 response options. Scores averaged with items 1 and 2 reverse scored.

Response options:

- 1= Strongly disagree
- 2= Slightly disagree
- 3= Neither
- 4= Slightly agree
- 5= Strongly agree

Motivation to be physically active

*How motivated are you to be physically active (e.g., walk, run, swim, cycle, dance, exercise, etc) **even when you are feeling knee pain?***

Scored via an 11-point NRS where. Range 0-10 where higher scores indicate greater motivation.

Response options: 0 = Not at all motivated – 10 = Very motivated

Knee Osteoarthritis Knowledge Scale

Each statement rated as False (1), Possibly False (2), Unsure (3), Possibly True (4), or True (5)

Numbers are not included in questionnaire, just there for scoring.

- 1. Your knee joint wears out with everyday use[^]*
- 2. Osteoarthritis will only get worse over time[^]*
- 3. Increased knee pain always means that you have damaged your knee[^]*
- 4. You need an X-ray or scan to know if you have osteoarthritis[^]*
- 5. Being active makes osteoarthritis feel better*
- 6. Keeping a healthy body weight is a key part of osteoarthritis care*

[^] item reverse scored

Scores range from 11-55 with higher scores indicating better knowledge.

7. *X-rays or scans show how much your osteoarthritis affects you[^]*
8. *Making your leg muscles stronger improves your ability to do daily tasks*
9. *Pain from osteoarthritis can be managed without surgery*
10. *Exercises can ease pain as much as most medications*
11. *Most people with knee osteoarthritis will need a joint replacement at some point[^]*

Perceived change *	
How much have your feelings of hope for the future changed since watching the video?
 
 – much less hopeful – somewhat less hopeful – no change – somewhat more hopeful – much more hopeful 	
Likert scale with 5 response options.
 
Responses dichotomised with participants indicating they are “somewhat more” or “much more” classified as ‘more hopeful’. All other respondents classified as ‘not more hopeful’.

Satisfaction that video met information needs *	
How satisfied are you that the video helped meet your current needs for information about your knee pain?
 
very unsatisfied moderately unsatisfied neutral moderately satisfied very satisfied
	
Likert scale with 5 response options. N (%) in each category

Perceived personal chance of ever needing knee replacement surgery	
How likely do you think you are of needing knee replacement surgery in the future?
 
1 = very unlikely to need surgery 2 = unlikely to need surgery 3 = neutral 4 = likely to need surgery 5 = very likely to need surgery
	
Likert scale with 5 response options. N (%) in each category

NRS = Numerical rating scale

* Only measured post-intervention (not baseline)

Appendix 2

DEFINITIONS OF DERIVED VARIABLES IN THE DATA SET

Variable in data set	Unit	Variable label in spreadsheet	Calculation	Range	Better
Arthritis Self Efficacy Scale – Pain Subscale	5 items, 0-10	ASES	Average	0-10	↑
Brief Fear of Movement Scale for Osteoarthritis	6 items, 1-4	BFMS	Summed	6-24	↓
Level of concern	Single item, 0-4 (ordinal)	Concern	n/a	0-4	↓
Credibility/expectation questionnaire – Part 1	3 items, 1-9	CEQp1	Summed	3-27	↑
Credibility/expectation questionnaire – Part 2	2 items, 1) 1-9 2) -4 to +4	CEQp2	Summed, item 2 transformed to 1-9	2-18	↑
Importance of physical activity	4 items, 1-5	ImpPA	Averaged, items 1 & 2 reverse scored	1-5	↑
Motivation to be physically active	Single item, 0-10	MotPA	n/a	0-10	↑
Knee osteoarthritis knowledge scale	11 items	KOAKS	Summed, items 1,2, 3, 4, 7, & 11 reverse scored.	11-55	↑
Likelihood of needing surgery	Single item, 1-5 (ordinal)	Surgery	n/a	1-5	↓
Perceived change in hope (binary, only measured post-intervention)	Single item, 5 levels	Hope	Dichotomised, 1-3 = not more	0 or 1	1

			hopeful (0), 4-5 = more hopeful (1)		
Satisfaction with meeting information needs	Single item, 5 levels (ordinal)	Satisfaction	n/a	1-5	↑

Table 1. Baseline characteristics of participants by group, reported as mean (standard deviation) unless otherwise stated.

Domain	Units / categories	Group 1 [N = xxx]	Group 2 [N = xxx]
Age	Years		
Gender, n (%)	Male Female Other / Prefer not to say Non-binary		
State/territory, n (%)	Australian Capital Territory New South Wales Northern Territory Queensland South Australia Tasmania Victoria Western Australia		
Geographical location ^a , n (%)	Major city Inner regional Outer regional Remote Very remote		
Height	Metres		
Weight	Kilograms		
Body mass index	kg/m ²		
Level of education, n (%)	<3 years of secondary education (high school) 3 or more years of secondary education (high school) Some education beyond high school e.g., trade/technical/vocational training Completed tertiary education (college or university)		
Current employment situation, n (%)	Unemployed/not employed/ e.g., full-time carer, full-time student Retired (not due to health reasons) Unable to work due to health reasons Paid work part time Paid work full time		
Ethnicity, n (%)	Australian/New Zealand Aboriginal and Torres Strait Islander European Asian Other Oceania North African & Middle Eastern Sub-Saharan Africa North American South American Other		
Pain severity during walking ^b	0-10		

Pain duration, n (%)	Less than one year	
	One to two years	
	Two to five years	
	Five to ten years	
	Ten to fifteen years	
	Fifteen to twenty years	
	More than twenty years	
	Where received OA information ^c , n (%)	No information received
	GP or family doctor	
Orthopaedic surgeon		
Another doctor (such as sports doctor or rheumatologist)		
Nurse		
Physiotherapist		
Osteopath		
Chiropractor		
OA rehabilitation programme		
Arthritis educator		
Arthritis support group		
Other people with OA		
Family or friends		
Internet/website		
Television		
Information booklets		
Training as a health professional		
Other media		
Other health professional		
Personal relevance ^d , n (%)	Not at all relevant	
	A little bit relevant	
	Quite relevant	
	Very relevant	
	Extremely relevant	

^a Australian Standard Geographical Classification (ASGC) Remoteness Structure.

^b Question asked participant to rate the “average amount of pain felt during walking over the PAST WEEK in your most painful knee.”

^c Multiple options may be selected.

^d Question asked participant to rate “How relevant do you think education about knee osteoarthritis is to you at this time?”

Table 2. Summary measures and estimated mean difference in change [95% CI] or relative risks [95% CI], risk differences [95% CI] or odds ratios [95% CI] for each outcome as appropriate between groups.

Outcome	Baseline, mean (SD)		Post-intervention, mean (SD)		Within-group change ^a , mean (SD)		Between-group difference in change (n=xxx)	
	Group 1 (n=xxx)	Group 2 (n=xxx)	Group 1 (n=xxx)	Group 2 (n=xxx)	Group 1 (n=xxx)	Group 2 (n=xxx)	Mean ^b [95% CI]	P-value
Primary outcomes								
ASES								
BFMS								
Secondary outcomes								
Credibility/expectancy questionnaire								
Part 1, range 3-27								
Part 2, range 2-18								
Importance of physical activity, range 1-5								
Motivation to be physically active, range 0-10								
Knee Osteoarthritis Knowledge Scale, range 11-55								
	Baseline, counts (proportions)		Post-intervention, counts (proportions)		Between-group (n=xxx)			

	Group 1 (n=xxx)	Group 2 (n=xxx)	Group 1 (n=xxx)	Group 2 (n=xxx)	Relative risk ^c [95% CI]	P-value	Risk difference ^d [95% CI]	P- value
Perceived change to more hopeful ^e	n/a	n/a						
	Baseline, counts (proportions)		Post-intervention, counts (proportions)		Between-group (n=xxx)			
	Group 1 (n=xxx)	Group 2 (n=xxx)	Group 1 (n=xxx)	Group 2 (n=xxx)	Odds ratio ^f [95% CI]	P-value	Relative risk ratio ^g [95% CI]	P- value
Level of concern ^h					OR [95% CI]	P	–	–
0=Not at all concerned					–	–	REFERENCE	–
1=A little concerned					–	–	RRR [95% CI]	P
2=Quite concerned					–	–	RRR [95% CI]	P
3=Very concerned					–	–	RRR [95% CI]	P
4=Extremely concerned					–	–	RRR [95% CI]	P
Perceived personal likelihood of ever needing knee replacement surgery					OR [95% CI]	P	–	–

1 = very unlikely to need surgery				–	–	REFERENCE	–
2 = unlikely to need surgery				–	–	RRR [95% CI]	P
3 = neutral				–	–	RRR [95% CI]	P
4 = likely to need surgery				–	–	RRR [95% CI]	P
5 = very likely to need surgery				–	–	RRR [95% CI]	P
Satisfaction that video met information needs				OR [95% CI]	P	–	–
1 = very unsatisfied	n/a	n/a		–	–	REFERENCE	–
2 = moderately unsatisfied	n/a	n/a		–	–	RRR [95% CI]	P
3 = neutral	n/a	n/a		–	–	RRR [95% CI]	P
4 = moderately satisfied	n/a	n/a		–	–	RRR [95% CI]	P
5 = very satisfied	n/a	n/a		–	–	RRR [95% CI]	P

^a Within-group change was calculated as post-intervention minus baseline for all continuous outcomes, except Brief Fear of Movement Scale for Osteoarthritis where the within-group change was calculated as baseline minus post-intervention, so that positive values indicate improvement.

^b Positive values favour Group 2. Mean (95% CI) difference in change between groups, adjusted for the outcome at baseline, estimated using separate regression models for each outcome.

^c Relative risks > 1 favour Group 2.

^d Risk differences > 0 favour Group 2.

^e Logistic regression model fitted, unadjusted.

^f Ordinal logistic regression models fitted, adjusted for the outcome at baseline where able, as proportional odds could be assumed. Odds ratios > 1 favour Group 2.

^g Multinomial regression models fitted, adjusted for the outcome at baseline where able, as proportional odds could not be assumed. Relative risk ratios > 1 favour Group 2.

^h Question asked “How concerned are you about your knee problem?”

SD = standard deviation.

ASES = Arthritis Self-efficacy Scale (Pain subscale); scored 0-10, with higher scores indicating greater self-efficacy.

BFMS= Brief Fear of Movement Scale for Osteoarthritis; scored 6-24, with higher scores indicating greater fear.

Appendix 1. Baseline characteristics and outcome summary measures of participants who did and did not complete both primary outcomes, reported as mean (standard deviation) unless otherwise stated.

Domain	Units / categories	Completed both primary outcomes [N = xxx]	Incomplete one or both primary outcomes [N = xxx]
Age	Years		
Gender, n (%)	Male		
	Female		
	Non-binary		
	Other (please specify)		
	Prefer not to say		
State/territory, n (%)	Australian Capital Territory		
	New South Wales		
	Northern Territory		
	Queensland		
	South Australia		
	Tasmania		
	Victoria		
	Western Australia		
Geographical location ^a , n (%)	Major city		
	Inner regional		
	Outer regional		
	Remote		
	Very remote		
Height	Metres		
Weight	Kilograms		
Body mass index	kg/m ²		
Level of education, n (%)	<3 years of secondary education (high school)		
	3 or more years of secondary education (high school)		
	Some education beyond high school e.g., trade/technical/vocational training		

	Completed tertiary education (college or university)
Current employment situation, n (%)	Unemployed/not employed/ e.g., full-time carer, full-time student
	Retired (not due to health reasons)
	Unable to work due to health reasons
	Paid work part time
	Paid work full time
Ethnicity, n (%)	Australian/New Zealand
	Aboriginal and Torres Strait Islander
	European
	Asian
	Other Oceania
	North African & Middle Eastern
	Sub-Saharan Africa
	North American
	South American
	Other
Pain severity during walking ^b	0-10
Pain duration, n (%)	Less than one year
	One to two years
	Two to five years
	Five to ten years
	Ten to fifteen years
	Fifteen to twenty years
	More than twenty years
Where received OA information ^c , n (%)	No information received
	GP or family doctor
	Orthopaedic surgeon
	Another doctor (such as sports doctor or rheumatologist)
	Nurse
	Physiotherapist
	Osteopath

	Chiropractor
	OA rehabilitation programme
	Arthritis educator
	Arthritis support group
	Other people with OA
	Family or friends
	Internet/website
	Television
	Information booklets
	Other
Personal relevance ^d , n (%)	Not at all relevant
	A little bit relevant
	Quite relevant
	Very relevant
	Extremely relevant
Arthritis Self-efficacy Scale (Pain subscale), range 0-10	
Brief Fear of Movement Scale for Osteoarthritis, range 6-24	
Credibility/expectancy questionnaire	Part 1, range 3-27
	Part 2, range 2-18
Importance of physical activity, range 1-5	
Motivation to be physically active, range 0-10	
Knee Osteoarthritis Knowledge Scale, range 11- 55	
Level of concern, n (%)	0=Not at all concerned
	1=A little concerned
	2=Quite concerned
	3=Very concerned
	4=Extremely concerned
Perceived personal likelihood of ever needing knee replacement surgery, n (%)	1 = very unlikely to need surgery

2 = unlikely to need surgery

3 = neutral

4 = likely to need surgery

5 = very likely to need surgery

^a Australian Standard Geographical Classification (ASGC) Remoteness Structure.

^b Question asked participant to rate the “average amount of pain felt during walking over the PAST WEEK in your most painful knee.”

^c Multiple options may be selected.

^d Question asked participant to rate “How relevant do you think education about knee osteoarthritis is to you at this time?”

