Statistical Analysis Plan (Short)

Comparative effect of two educational videos for people with knee osteoarthritis (vidEO): An online randomised controlled trial

Version: 2

Author/s of SAP: [name] and [name] (Biostatisticians, Centre for Epidemiology and Biostatistics), University of Melbourne
[name], CHESM, University of Melbourne

Date of SAP: 14/12/2021

Author/s of template: [name] (Deputy Head MISCH Biostatistics), University of Melbourne (Template adapted from www.pfizer.com)

Date of template: 25/10/2021

[figure not shown]
Table of Contents

1 Introduction	3
2 Data Source	4
3 Analysis Objectives.....	5
3.1 Aim 1	5
3.2 Aim 2	5
3.3 Aim 3	5
4 Analysis sets/Populations/Subgroups.....	5
5 Endpoints and Covariates	6
6 Handling of Missing Values and Other Data Conventions	6
7 Statistical Methodology	7
7.1 Statistical Procedures.....	7
7.1.1 Aim 1	7
7.1.2 Aim 2	7
7.1.3 Aim 3	Error! Bookmark not defined.
7.2 Measures to Adjust for Multiplicity, Confounders, Heterogeneity	8
8 Sensitivity Analyses	8
9 QC Plans	8
10 Programming Plans	8
11 References	8
Appendix 1	9
Appendix 2	16
Appendix 3	18

1 Introduction

Objectives	To determine if an educational video based on an empowerment and participatory discourse improves self-efficacy to manage knee OA pain and reduced fear of movement more than an educational video based on a disease information and impairment discourse, among people with knee osteoarthritis symptoms.
Study Design	Two-arm, parallel groups superiority randomised controlled trial
Planned Sample Size	516
Study Procedures	Our trial will be delivered via an online survey (Qualtrics, Provo, UT, USA) and Vimeo (Vimeo Inc, NYC, USA) video sharing platform. Volunteers will be recruited by a digital survey-based research company (Cint PTY LTD) and complete an online screening survey. Eligible participants will then be invited to read the information sheet and digitally consent to participate in the study. They will provide demographic information and answer the baseline questionnaires. They will then be randomised to one of two intervention groups. On the next page of the survey they will be presented with a video to watch before moving on the post-intervention questionnaire.
Duration of the study	Anticipated participant recruitment start: November 2021 Anticipated data collection end: December 2021 Recruitment for this study is anticipated to take approximately 3-4 weeks.

Figure 1. Study chart

2 Data Source

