Participant recruitment will be managed by an external company, Cint PTY LTD. Data security will be managed according to their data privacy and security protocols.

Data collection will be managed wholly online through Qualtrics, an electronic data capture system. Qualtrics is a secure web application for building and managing research questionnaires and databases. The University of Melbourne holds a licence for staff use of Qualtrics and surveys and associated data will only be accessible via secure login by the study research staff.

Re-identifiable/coded data

Questionnaires will be completed electronically and anonymously, with no identifying information being recorded. Electronic data will be stored in the Qualtrics website, accessible only to the study research staff by password protection. Data from within Qualtrics will eventually be exported to Microsoft Excel and other statistical packages used by the researchers for analyses and stored securely on password-protected servers accessible only to the study research staff.

3 Analysis Objectives

The aim of this randomised controlled trial (RCT) is to compare the effect of two knee OA educational videos on people with knee OA.

3.1 Aim 1

The primary hypotheses are that a knee OA educational video based on an empowerment discourse and emphasising participation in effective lifestyle behaviours will lead to 1) feeling more confident to self-manage knee OA pain, and 2) having less fear of movement, compared to an educational video based on a disease information and impairment discourse.

3.2 Aim 2

We secondarily hypothesise that after watching the novel educational video, people with knee OA will have reduced levels of concern, more positive expectations about their knee OA prognosis and the benefit to be gained from physical activity, will be more motivated to be physically active, and will have at least as accurate beliefs about knee OA disease.

3.3 Aim 3

N/A

4 Analysis sets/Populations/Subgroups

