5.1 Primary Outcomes

- Change in Arthritis Self Efficacy Scale – Pain Subscale (post-intervention minus baseline),
- Change in Brief Fear of Movement Scale for Osteoarthritis (baseline minus post-intervention).

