7.1 Statistical Procedures

A biostatistician ([name], supervised by [name]) will analyse de-identified data in Stata version 16.1 (StataCorp LLC, College Station, TX, USA), while blind to group allocation. Descriptive data will be presented by intervention group as mean (SD), median (IQR) or n (%) as appropriate. Comparative analyses between groups will be performed using intention-to-treat according to the group to which the participant was randomised, irrespective of whether they adhered to the intervention. The number included in each analysis will be reported. Standard diagnostic plots will be used to check model assumptions, including assessing linearity and homoscedasticity, where appropriate.

7.1.1 Aim 1

Separate linear regression models for each primary outcome will be used to estimate the between-group mean (95% CI) difference in change scores (either baseline minus post-intervention or post-intervention minus baseline, so that positive values favour the experimental group (allocated the 'empowerment and participatory discourse' video), adjusted for the outcome at baseline. Post-intervention time point was 'immediately following watching the video'.

7.1.2 Aim 2

Separate linear regression models for each continuous secondary outcome will be used to estimate the between-group mean (95% CI) difference in change scores (post-intervention minus baseline, so that positive values favour the experimental 'empowerment and participatory discourse' group), adjusted for the outcome at baseline. For the binary secondary outcome, perceived change, groups will be compared using logistic regression, with results reported as risk differences and risk ratios, with corresponding 95% CIs. For ordinal secondary outcomes, ordinal logistic regression models will be fitted similarly, adjusted for the outcome at baseline where able. The proportional odds

assumption will be assessed using the Brant test. If proportional odds cannot be assumed, multinomial regression models will be fitted. Results will be reported as odds ratios, or relative risk ratios if multinomial regression is used, with corresponding 95% CIs.

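### The fixed 0.025 test level for each primary outcome is valid, but Holm's step-down rule gives more power at the same 5% familywise error

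*SAP*

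**What the plan says.** Section 3.1 states two primary hypotheses, both in favour of the empowerment video: it "will lead to 1) feeling more confident to self-manage knee OA pain, and 2) having less fear of movement". Section 5.1 names the matching outcomes, the change in the arthritis self-efficacy pain subscale and the change in the brief fear of movement scale.

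Section 7.1.1 tests them one at a time: "Separate linear regression models for each primary outcome will be used to estimate the between-group mean (95% CI) difference in change scores". Section 7.2 then sets the error control. The authors have "adjusted the alpha for each primary outcome to 0.025 to give an overall alpha of 0.05 across both outcomes". Secondary outcomes are called exploratory and are left unadjusted.

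No step-down, hierarchical or alpha-recycling rule appears anywhere in the SAP. Each primary outcome is therefore judged at 0.025 whatever the other one shows.

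**The concern.** Once one of two hypotheses has been rejected at 0.025, only one can still be falsely rejected, and 0.05 is available for testing it. A fixed 0.025 leaves that allowance unused. The plan expects benefit on both outcomes, which is the setting where it would be used most often.

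For example, suppose the trial finds p = 0.001 for self-efficacy and p = 0.04 for fear of movement. Under 7.2 as written, the fear-of-movement hypothesis is not supported. Under Holm both are supported, at the same overall 5% error rate and with the same participants. What is at stake is the claim on the second primary outcome.

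**Working it through.** **The plan's own figure.** 0.025 + 0.025 = 0.05, as stated. If the two tests were independent, the exact figure would be 1 − (1 − 0.025)² = 0.0494. The control claimed in 7.2 is correct.

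**Holm has the same control.**
- Both nulls true: any false rejection needs the smaller p to be at or below 0.025. The probability of that is at most 0.025 + 0.025 = 0.05.
- One null true: a false rejection needs that outcome's own p to be at or below 0.05, so the probability is at most 0.05.

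Neither step uses the correlation between outcomes.

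**Inputs for the power comparison.** From the SAP: two outcomes, 0.025 each, 0.05 overall (7.2), tested in separate models (7.1.1). Assumed, because the SAP does not state them: two-sided tests, power per outcome at 0.025 of 80% or 90%, and correlation rho between the two test statistics of 0 to 0.7. Power is assumed directly, so no effect size, SD or allocation ratio is needed.

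**Hand check at rho = 0, 80% power.**
- Mean of the test statistic: z(0.9875) + z(0.80) = 2.241 + 0.842 = 3.083.
- Power of the same test at 0.05: Φ(3.083 − 1.960) = Φ(1.123) = 0.869.
- Chance that p lies between 0.025 and 0.05: 0.869 − 0.800 = 0.069.
- Per outcome under Holm: 0.800 + 0.069 × 0.800 = 0.855.
- Both outcomes, Bonferroni: 0.80² = 0.640.
- Both outcomes, Holm (both p at or below 0.05, less the case where neither is at or below 0.025): 0.869² − 0.069² = 0.750, or 0.751 with unrounded inputs.
- At least one outcome, either rule: 1 − 0.20² = 0.960.

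**Range by simulation** (4 million pairs of correlated normal test statistics per row):

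| Power per outcome at 0.025 | rho | Per outcome, Holm | Both: Bonferroni → Holm | At least one, either rule |
|---|---|---|---|---|
| 80% | 0 | 85.6% | 64.1% → 75.1% | 96.0% |
| 80% | 0.5 | 84.6% | 68.7% → 77.8% | 91.3% |
| 80% | 0.7 | 84.0% | 71.3% → 79.4% | 88.7% |
| 90% | 0 | 93.7% | 81.0% → 88.4% | 99.0% |
| 90% | 0.5 | 93.1% | 83.3% → 89.4% | 96.8% |
| 90% | 0.7 | 92.7% | 84.7% → 90.1% | 95.3% |

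With unequal power of 90% and 50%, the weaker outcome rises from 50% to about 60%.

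**Simulated familywise error.** With both nulls true, the two rules give the same figure: 0.049 at rho 0 and 0.043 at rho 0.7. With one null true and the other outcome always rejected, Holm gives 0.050 and Bonferroni 0.025. The extra power comes from this unused allowance.

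**The case against.** The strongest reply is that nothing here is wrong. The rule is pre-specified, conservative and correctly computed, and many sound trials use it. That stands: this is an improvement in efficiency, not the repair of an error.

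A reader might infer more, namely that the trial must succeed on both outcomes and that 7.2 puts that success out of reach. The SAP does not support this. It lists two hypotheses, splits alpha between them and nowhere requires both to be significant. The chance of at least one positive primary outcome is the same under either rule. Nor can it be inferred that 516 is too few. The basis of that number is not given in the SAP, and if each outcome was powered at 0.025, each already has its target power.

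A second reply is that Bonferroni has simple matching simultaneous intervals (97.5% CIs), and Holm does not. The point is true in general but carries little weight here, because 7.1.1 and Table 2 plan 95% CIs for the primary outcomes. The plan as written does not use that advantage.

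A third is timing. The SAP is dated 14/12/2021, with data collection expected to end that month. A move to a more lenient rule so late is acceptable only if it is shown to precede unblinding. That stands and is part of the fix.

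**Conclusion.** The point holds as a cheap improvement to a valid rule. Holm supports every claim that 7.2 supports and adds one only when one p is at or below 0.025 and the other lies between 0.025 and 0.05.

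Under assumed equal power of 80% to 90% and rho of 0 to 0.7, the gain is about 3 to 6 percentage points per outcome and about 5 to 11 points for showing both. It is zero for showing at least one. These sizes are illustrative, because the SAP gives no power, effect size, SD, correlation or allocation ratio. That Holm is never less powerful, at the same 5% error under any correlation, rests on none of these assumptions.

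**What to change.** In 7.2, replace the fixed rule with Holm: compare the smaller of the two primary p-values with 0.025 and, only if it is rejected, compare the larger with 0.05.

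In Table 2, report Holm-adjusted p-values for the two primary outcomes, to be read against 0.05. The adjusted smaller p is twice the smaller p. The adjusted larger p is the greater of that value and the larger p itself. In the example above, 0.001 and 0.04 become 0.002 and 0.04.

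For the intervals, choose one of two options:
- Leave the planned 95% CIs in 7.1.1 and Table 2, with a footnote that they are unadjusted and that significance is judged by the Holm-adjusted p-values.
- Add 97.5% CIs as conservative simultaneous intervals, with a footnote that one may include zero for an outcome declared at the second step.

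Date and document the change before unblinding. Because 7.1 has the analyst run comparisons while blind to group, it is best recorded before any between-group p-value is produced.

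The cost is a short edit to 7.2, Table 2 and its footnotes, plus 7.1.1 if 97.5% CIs are added. The planned 516 participants need not change. The one downside is that Holm has no simple matching simultaneous intervals, which the footnote covers.
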